10.1.3 Reporting to the FDA

The conduct of the study will comply with all FDA safety reporting requirements. **PLEASE NOTE THAT REPORTING REQUIREMENTS FOR THE FDA DIFFER FROM REPORTING REQUIREMENTS FOR HRPO/QASMC.** It

is the responsibility of the Washington University Sponsor-Investigator to report to the FDA as follows:

- Report any unexpected fatal or life-threatening suspected adverse reaction (refer to Appendix C for definitions) no later than **7 calendar days** after initial receipt of the information.
- Report a suspected adverse reaction that is both serious and unexpected (SUSAR, refer to Appendix C) no later than **15 calendar days** after it is determined that the information qualifies for reporting. Report an adverse event (refer to Appendix C) as a suspected adverse reaction only if there is evidence to suggest a causal relationship between the drug and the adverse event, such as:
 - A single occurrence of an event that is uncommon and known to be strongly associated with drug exposure
 - One or more occurrences of an event that is not commonly associated with drug exposure but is otherwise uncommon in the population exposed to the drug
 - An aggregate analysis of specific events observed in a clinical trial that indicates those events occur more frequently in the drug treatment group than in a concurrent or historical control group
- Report any findings from epidemiological studies, pooled analysis of multiple studies, or clinical studies that suggest a significant risk in humans exposed to the drug no later than **15 calendar days** after it is determined that the information qualifies for reporting.
- Report any findings from animal or in vitro testing that suggest significant risk in humans exposed to the drug no later than **15 calendar days** after it is determined that the information qualifies for reporting.
- Report any clinically important increase in the rate of a serious suspected adverse reaction of that listed in the protocol or IB within **15 calendar days** after it is determined that the information qualifies for reporting.

Submit each report as an IND safety report in a narrative format or on FDA Form 3500A or in an electronic format that FDA can process, review, and archive. Study teams must notify the Siteman Cancer Center Protocol Development team of each potentially reportable event within 1 business day after initial receipt of the information, and must bring the signed 1571 and FDA Form 3500A to the Siteman Cancer Center Protocol Development team no later than 1 business day prior to the due date for reporting to the FDA.

Each notification to FDA must bear prominent identification of its contents (“IND Safety Report”) and must be transmitted to the review division in the Center for Drug Evaluation and Research (CDER) or in the Center for Biologics Evaluation and Research (CBER) that has responsibility for review of the IND. Relevant follow-up information to an IND safety report must be submitted as soon as the

information is available and must be identified as such (“Follow-up IND Safety Report”).

10.1.1 Reporting to Secondary Sites

The Washington University Sponsor-Investigator (or designee) will notify the research team at each secondary site of all unanticipated problems involving risks to participants or others that have occurred at other sites within **10 working days** of the occurrence of the event or notification of the Sponsor-Investigator (or designee) of the event. This includes events that take place both at Washington University and at other secondary sites, if applicable. Refer to Section 16.0 (Multicenter Regulatory Requirements) for more information.

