5.0 STUDY TREATMENT

5.1 Overview

Patients will be randomly assigned in a double-blind fashion to receive either duvelisib 25mg or placebo twice daily for up to 10 days. Patients who have significant clinical improvement prior to day 10 and are going to be discharged from the hospital may discontinue the treatment early with investigator permission.

Blocks of 10 patients will be used to allocate patients to duvelisib or placebo. Due to differences in color between the duvelisib and placebo capsules, we will employ methods in this trial to maintain the blinding of the investigator to the best of our ability (e.g. having the drug dispensed by alternative personnel). If this study were to lead to a pivotal trial, matched placebos would be manufactured for such a trial.

Treatment is dosed orally and can be administered with or without food. For patients unable to administer orally, a duvelisib suspension will be administered through a nasogastric/orogastric tube. In this event, the capsule(s) will be opened and the dose will be placed in 40mL water and stirred until dissolved. The suspension should be administered using an appropriate syringe within 6 hours after preparation. Following administration, the tube should be rinsed with approximately 75 mL of water.

If a dose is missed by fewer than 6 hours, administer the missed dose right away and take the next dose as usual. If a dose is missed by more than 6 hours, the patient should not take an additional dose, but should take the next usual prescribed dose.

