10.2 Secondary Site Reporting Requirement

The research team at each secondary site is required to promptly notify the Washington University Sponsor-Investigator and designee of all serious adverse events (refer to Appendix F, Section D) within **1 working day** of the occurrence of the event or notification of the secondary site’s PI of the event. This notification may take place via email if there is not yet enough information for a formal written report (using a FDA Form 3500a (MedWatch) and Washington University’s cover sheet (Appendix H)). A formal written report must be sent to the Washington University Sponsor-Investigator and designee within **4 calendar days** (for fatal or life-threatening suspected adverse reactions) or **11 calendar days** (for serious unexpected adverse reactions) of the occurrence of the event or notification of the secondary site’s PI of the event.

The research team at a secondary site is responsible for following its site’s guidelines for reporting applicable events to its site’s IRB according to its own institutional guidelines. The research team at Washington University is responsible for reporting all applicable events to the FDA and AstraZeneca as needed.

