12.0 STATISTICAL CONSIDERATIONS

This is a double-blinded randomized pilot phase II study. The purpose of this study is to provide hypothesis generating data on the efficacy and toxicity duvelisib for the treatment of COVID-19. The total accrual goal is 28 patients, approximately 14 in each arm. Blocks of 10 patients will be used to allocate patients to either duvelisib or placebo. The projected enrollment time frame is 3 months (approximately 9 patients per month).

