APPENDIX D: Reporting Timelines

Expedited Reporting Timelines			
Event	HRPO	FDA	Verastem Oncology
Serious AND unexpected suspected adverse reaction		Report no later than 15 calendar days after it is determined that the information qualifies for reporting	Report to Verastem at the same time as the FDA.
Unexpected fatal or life-threatening suspected adverse reaction		Report no later than 7 calendar days after initial receipt of the information	Report to Verastem at the same time as the FDA.
Unanticipated problem involving risk to participants or others	Report within 10 working days. If the event results in the death of a participant enrolled at WU/BJH/SLCH, report within 1 working day.		Report to Verastem at the same time as the FDA.
Pregnancy (within 30 days after last dose)			Report to Verastem at the same time as the FDA.
Overdose			Report to Verastem at the same time as the FDA.
Major deviation	Report within 10 working days. If the event results in the death of a participant enrolled at WU/BJH/SLCH, report within 1 working day.		
A series of minor deviations that are being reported as a continuing noncompliance	Report within 10 working days.		
Protocol exception	Approval must be obtained prior to implementing the change		
Clinically important increase in the rate of a serious suspected adverse reaction of that list in the protocol or IB		Report no later than 15 calendar days after it is determined that the information qualifies for reporting	Report to Verastem at the same time as the FDA.
Complaints	If the complaint reveals an unanticipated problem involving risks to participants or others OR noncompliance, report within 10 working days. If the event results in the death of a participant enrolled at WU/BJH/SLCH,		

Expedited Reporting Timelines			
Event	HRPO	FDA	Verastem Oncology
	report within 1 working day. Otherwise, report at the time of continuing review.		
Breach of confidentiality	Within 10 working days.		
Incarceration	If withdrawing the participant poses a safety issue, report within 10 working days. If withdrawing the participant does not represent a safety issue and the patient will be withdrawn, report at continuing review.		

Routine Reporting Timelines			
Event	HRPO	FDA	Verastem Oncology

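### Notice to secondary sites of a fatal or life-threatening unanticipated problem may take 10 working days, longer than the 10-day treatment course

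*Combined protocol and SAP*

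**What the plan says.** Two subsections are numbered 10.1.1. The second, Reporting to Secondary Sites, requires the Sponsor-Investigator to notify "each secondary site of all unanticipated problems involving risks to participants or others that have occurred at other sites within 10 working days". The clock runs from the event or from the Sponsor-Investigator hearing of it. The duty covers "each secondary site of all unanticipated problems involving risks to participants or others", and fatal or life-threatening ones have no line of their own. The section sends the reader to a Section 16.0 that does not exist; the multicenter section is 13.0.

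Section 5.1 assigns patients "to receive either duvelisib 25mg or placebo twice daily for up to 10 days".

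The other reporting limits are:

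- **Secondary site to coordinating centre (Section 10.2):** notice "of all serious adverse events (refer to Appendix F, Section D) within 1 working day of the occurrence of the event" or of the site investigator's learning of it. E-mail is allowed while details are incomplete.
- **HRPO (Appendix D):** 10 working days for an unanticipated problem, but "If the event results in the death of a participant enrolled at WU/BJH/SLCH, report within 1 working day".
- **FDA (Section 10.1.3):** 7 calendar days for an unexpected fatal or life-threatening suspected reaction; 15 calendar days after determination for one that is serious and unexpected.
- **Drug maker:** 24 hours in Section 10.1.2; simultaneous with the FDA in Appendix D.
- **Participating sites (Section 13.0):** the coordinating centre passes on reportable adverse events, with no time limit.
- **Participating sites (Section 12.3):** notice if the study is discontinued, again with no time limit.

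Section 12.0 gives the accrual: "The projected enrollment time frame is 3 months (approximately 9 patients per month").

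**The concern.** The clinicians at the secondary site are among those who can act on news of a grave, unexpected event. They obtain consent, monitor patients and judge whether new events are related to treatment. Section 5.2 makes the handling of several events (Grade 2 pneumonitis, viral load elevation, other Grade 3 events) turn on suspected relatedness, and Section 5.4 relies on clinical judgement. A clinician who does not know of a similar event at the other site makes those judgements with less information.

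If the limit for telling the site is longer than the course, the Sponsor-Investigator can follow the protocol exactly while patients there are consented, dosed and finished before their doctors hear of the event.

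**Working it through.** The plan gives no figure of its own to reproduce; the check is calendar arithmetic.

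**1. Length of the limit.** The protocol does not define a working day, so I assume Monday to Friday. Calendar days from the event to the end of the tenth working day:

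| Counting rule | No holiday | One public holiday |
|---|---|---|
| Event day not counted | 14 (Mon–Fri), 13 (Sat), 12 (Sun) | 15–17 |
| Event day counted if a working day | 11–13 | 14–16 |

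The range is 11 to 17, with 14 for a weekday event, event day not counted, no holiday. If the clock starts when the Sponsor-Investigator is notified, the delay from the event itself can be longer.

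**2. Comparison with the course.** I take the course as at most 10 consecutive calendar days. A patient on treatment day k at the event reaches day 10 after 10 − k days, so at most 10 − 1 = 9 days later. Against limits of 11, 14 and 17 days, the last such patient finishes 2, 5 and 8 days before notice is due. With a 14-day limit, a patient who starts s days after the event reaches day 10 at s + 9, which is before the deadline for s up to 4.

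**3. Patients in the window.** Accrual is 28 patients in 3 months: 28/3 = 9.3 per month, matching the stated figure of about 9, or 28/91 = 0.308 per day.

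- Randomised trial-wide in 14 days: 14 × 0.308 = 4.3, of whom about half (2.2) receive duvelisib.
- On treatment trial-wide at any time, with full courses: 10 × 0.308 = 3.1, about 1.5 on duvelisib.
- Randomised trial-wide in 1 working day (1 to 3 calendar days): 0.3 to 0.9.

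The documents give no split by site. If the secondary site enrolled 20% to 50% (an assumption), it would have 0.9 to 2.2 new patients in 14 days, 0.4 to 1.1 of them on duvelisib. It would also have 0.6 to 1.5 patients already on treatment, 0.3 to 0.8 of them on duvelisib.

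**4. Limits for one event.** Take a death at Washington University that is both an unanticipated problem and an unexpected suspected reaction.

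| Recipient | Limit |
|---|---|
| Drug maker | 24 hours (Section 10.1.2), or with the FDA (Appendix D) |
| HRPO | 1 working day |
| FDA | 7 calendar days |
| Secondary site | 10 working days |

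**5. Other routes to the site.** Sections 12.3 and 13.0 set no time. Appendix D has columns only for HRPO, the FDA and the drug maker, so its shorter limits do not reach the site.

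**The case against.** The limit is a ceiling, not a planned delay. Earlier notice is allowed, Section 13.0 adds a general duty to pass on reportable events together with regular calls, and no document demands a faster limit. All of that stands. It makes this a gap in what is guaranteed, not a forecast of what will happen.

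A reader might infer that secondary sites have the slowest limit in the protocol. They do not. For non-fatal unanticipated problems HRPO has the same 10 working days, and the FDA's 15 calendar days for serious unexpected reactions can be longer. The shortfall is confined to fatal and life-threatening events.

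A reader might infer that any drug-related death falls under this limit. It does so only if the death is an unanticipated problem. Section 6.1.7 already warns of fatal colitis, cutaneous reactions and pneumonitis, so a death of a listed kind may not qualify.

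A reader might also infer that the DSMB learns nothing between scheduled reports. Section 11.0 leaves further DSMB duties to a charter that is not among the documents, so this cannot be concluded.

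Finally, the upward limit of 1 working day in Section 10.2 applies to serious adverse events as they arise, whereas an unanticipated problem has first to be classified. That is a reason not to impose 1 working day on every unanticipated problem. It weighs less for fatal or life-threatening ones, because Section 10.1.3 already has an internal office told of potentially reportable events within 1 business day.

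**Conclusion.** The concern holds for unanticipated problems that are fatal or life-threatening. The protocol allows 10 working days to tell the secondary site, and under every counting convention tried this exceeds the 10-day course. All patients on treatment there at the time of the event can finish before notice is due.

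The number affected is small. About 4.3 patients are randomised trial-wide in 14 days, roughly half to duvelisib, and the secondary site's share is unknown. These counts rest on the projected accrual and roughly equal allocation; the comparison of limit with course rests on neither. That Missouri Baptist Medical Center is the secondary site is inferred from the two-site list in the protocol summary.

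The primary analysis is untouched. This is an inexpensive safety improvement and should be made.

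**What to change.** In Reporting to Secondary Sites, split the limit in two:

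- Unanticipated problems that are fatal or life-threatening: notify secondary sites within 1 working day of the Sponsor-Investigator's awareness, by preliminary e-mail (the route Section 10.2 already allows in the other direction), with a follow-up report when details are available.
- All other unanticipated problems: notify secondary sites no later than HRPO is told.

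Add one secondary-site column to Appendix D carrying these same two limits, so that text and grid agree. In the same edit, point the section to 13.0 instead of 16.0, and reconcile the two limits for the drug maker in Section 10.1.2 and Appendix D.

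The cost is a wording change and one e-mail per event. The downside is that some early notices will be preliminary and need follow-up.

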10.2 Secondary Site Reporting Requirement

The research team at each secondary site is required to promptly notify the Washington University Sponsor-Investigator and designee of all serious adverse events (refer to Appendix F, Section D) within **1 working day** of the occurrence of the event or notification of the secondary site’s PI of the event. This notification may take place via email if there is not yet enough information for a formal written report (using a FDA Form 3500a (MedWatch) and Washington University’s cover sheet (Appendix H)). A formal written report must be sent to the Washington University Sponsor-Investigator and designee within **4 calendar days** (for fatal or life-threatening suspected adverse reactions) or **11 calendar days** (for serious unexpected adverse reactions) of the occurrence of the event or notification of the secondary site’s PI of the event.

The research team at a secondary site is responsible for following its site’s guidelines for reporting applicable events to its site’s IRB according to its own institutional guidelines. The research team at Washington University is responsible for reporting all applicable events to the FDA and AstraZeneca as needed.

10.3 Exceptions to Expedited Reporting

Events that do not require expedited reporting as described in Section 10.1 include:

- planned hospitalizations
- hospitalizations < 24 hours
- respite care
- events related to disease progression

Events that do not require expedited reporting must still be captured in the EDC.

11.0 DATA AND SAFETY MONITORING

In compliance with the Washington University Institutional Data and Safety Monitoring Plan, an independent Data and Safety Monitoring Board (DSMB) will be specifically convened for this trial to review toxicity data. A DSMB will consist of no fewer than 3 members including 2 clinical investigators and a biostatistician. DSMB members must be employed by Washington University, Barnes-Jewish Hospital, or St. Louis Children's Hospital. Like investigators, DSMB members are subject to the Washington University School of Medicine policies regarding standards of conduct. Individuals invited to serve on the DSMB will disclose any potential conflicts of interest to the trial principal investigator and/or appropriate university officials, in accordance with institution policies. Potential conflicts that develop during a trial or a member's tenure on a DSMB must also be disclosed.

The DSM report for the DSMB will be prepared by the study team with assistance from the study statistician and will be reviewed by the DSMB. The first DSM report will be completed 3 months or following the completion of the 10th enrollment, whichever comes first. Subsequent reports will be completed every 3 months thereafter or after completion of the 20th and 28th enrollments, whichever is sooner for as long as patients are actively receiving treatment on study. The DSM report will include:

- HRPO protocol number, protocol title, Principal Investigator name, data coordinator name, regulatory coordinator name, and statistician
- Date of initial HRPO approval, date of most recent consent HRPO approval/revision, date of HRPO expiration, date of most recent QA audit, study status, and phase of study
- History of study including summary of substantive amendments; summary of accrual suspensions including start/stop dates and reason; and summary of protocol exceptions, error, or breach of confidentiality including start/stop dates and reason
- Study-wide target accrual and study-wide actual accrual including numbers from participating sites
- Protocol activation date at each participating site
- Average rate of accrual observed in year 1, year 2, and subsequent years at each participating site
- Expected accrual end date and accrual by site
- Objectives of protocol with supporting data and list the number of participants who have met each objective
- Measures of efficacy
- Early stopping rules with supporting data and list the number of participants who have met the early stopping rules
- Summary of toxicities at all participating sites
- Abstract submissions/publications
- Summary of any recent literature that may affect the safety or ethics of the study

Further DSMB responsibilities are described in the DSMB charter.

12.0 STATISTICAL CONSIDERATIONS

This is a double-blinded randomized pilot phase II study. The purpose of this study is to provide hypothesis generating data on the efficacy and toxicity duvelisib for the treatment of COVID-19. The total accrual goal is 28 patients, approximately 14 in each arm. Blocks of 10 patients will be used to allocate patients to either duvelisib or placebo. The projected enrollment time frame is 3 months (approximately 9 patients per month).

12.1 Determination of Sample Size

The primary endpoint is 28 day overall survival (OS). While outcomes data are still developing, observational studies in other areas demonstrate 28-day OS to be poor but highly variable, from approximately 10-40%. [12–14] The variability in outcomes makes a priori sample size calculations difficult, but as this pilot study is designed to generate hypotheses rather than show superiority, sample size considerations were based largely on feasibility and detecting a clinically meaningful effect rather than statistical significance. For duvelisib to have clinically meaningful efficacy, we estimate that 28-day OS is >60% in this patient population. Based on this assumption, a sample size of 28, 14 in each arm, would allow us to detect an improvement in 28-day OS from approximately 20% to 60%, with >80% power at a one-sided type I error of <0.20. If 28 day survival in the placebo cohort is considerably higher, for example 40%, we would only have approximately 40% power in detecting a statistical-significant difference. In either event, additional confirmatory studies that are adequately powered would be needed to more accurately assess the efficacy of duvelisib for the treatment of COVID-19.

12.2 Statistical Analysis Plan

The primary endpoint is 28 day overall survival (OS) and will be treated as a binary outcome for the purposes of the primary analysis and will be described using descriptive statistics with the corresponding 95% confidence intervals. This will be an intent-to-treat analysis, and all patients randomized will be included in the analysis. The assumption is that all patients will be followed for at least 28 days. Patients who are lost to follow-up for any reason prior to this point will be included in the analysis and considered treatment failures and treated the same as a death. The 28 day OS of each cohort, duvelisib versus placebo, will be compared using Fisher's exact test of independence.

In addition to the primary analysis, OS will be treated as a time-to-event variable and will be described using Kaplan-Meier product limit estimators of event time curves and, if reached, medians with 95% confidence intervals. Cox proportional hazards models may be used to adjust for potential confounding effects. These analyses are considered exploratory, and we acknowledge that the proposed sample size will have low power for such adjustment.

The analyses of secondary end points are all exploratory in nature. Secondary endpoints of efficacy include: hospital and ICU length of stay and duration of ventilator (for those on a ventilator at the time of randomization), vasopressors, and renal replacement therapy. Kaplan-Meier product limit estimators of event time curves and, if reached, medians with 95% confidence intervals, and compared between cohorts using the Log-Rank test. For these analyses, patients will be censored at Day 28 or at death, whichever is earlier. Secondary end points of toxicity are viral kinetics and adverse events. The rate of viral load elevation and other adverse events of interested will be summarized using descriptive statistics and compared using Fisher's Exact tests.

Demographic and clinical characteristics of the sample and of each cohort will be summarized using descriptive statistics. For continuous variables, the number of patients, mean, standard deviation, median, minimum, maximum, and quartiles will be provided. For categorical variables, the number and percent of patients in each demographic/characteristic category will be summarized with 95% confidence intervals.

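### Boschloo's exact test would raise power from 83% to 90% and from 40% to 55% within the plan's own error limit; separately, 12.2 should state the one-sided 0.20 level

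*Combined protocol and SAP*

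**What the plan says.** Section 12.0 sets the size: "The total accrual goal is 28 patients, approximately 14 in each arm". It also sets the allocation: "Blocks of 10 patients will be used to allocate patients to either duvelisib or placebo".

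Section 12.1 describes 28-day survival in earlier observational studies as "poor but highly variable, from approximately 10-40" per cent. It says the sample "would allow us to detect an improvement in 28-day OS from approximately 20% to 60" per cent, "with >80% power at a one-sided type I error of <0.20". If placebo survival is 40%, it concedes that "we would only have approximately 40% power in detecting a statistical-significant difference".

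Section 12.2 makes the endpoint binary: "The primary endpoint is 28 day overall survival (OS) and will be treated as a binary outcome for the purposes of the primary analysis". It then names the test: "The 28 day OS of each cohort, duvelisib versus placebo, will be compared using Fisher's exact test of independence". It gives no side and no significance level for that test. The only level attached to the primary endpoint in 12.2 is the 95% of the descriptive confidence intervals.

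**The concern.** There are two separate points.

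**Efficiency.** Fisher's test conditions on the total number of survivors. With 14 per arm few outcomes are possible for each total, so its true error sits well below the nominal level. The sponsor accepted a one-sided error of up to 0.20, and the named test uses little more than half of it. The power lost matters most at the top of the plan's own range for control survival, where 12.1 already concedes a low figure.

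**Drafting.** The design level stands in 12.1 and the test in 12.2, and they are not joined. An analyst working from 12.2 alone could run a two-sided test, perhaps at 0.05 to match the intervals. The power would then be well short of what 12.1 states.

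**Working it through.** **Inputs.** Arms of 14 and 14 (12.0, 12.1); one-sided error limit 0.20 (12.1); survival 20% v 60% and 40% v 60% (12.1); control range 10-40% (12.1); Fisher's exact test (12.2). Patients lost to follow-up count as deaths (12.2), so the denominators stay at 14.

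**Method.** Let *x* and *y* be survivors on duvelisib and placebo, each from 0 to 14, giving 15 × 15 = 225 outcomes.

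- One-sided Fisher p-value: P(X ≥ x), with X hypergeometric (28 patients, x + y survivors, 14 on duvelisib).
- Power: the sum over rejected outcomes of Bin(x; 14, p₁) × Bin(y; 14, p₀).
- Size: the same sum with p₁ = p₀ = p, maximised over a fine grid of p.
- Boschloo: rank outcomes by the Fisher p-value and take the largest cut-off whose size is at most 0.20.

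**Step 1: the plan's figures.** One-sided Fisher at 0.20 gives 82.7% (20% v 60%) and 40.1% (40% v 60%). Both statements in 12.1 reproduce. They do not identify the level uniquely: one-sided Fisher at 0.15 gives 81.4% and 39.9%.

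**Step 2: true error of that test.** The maximum is 0.111, at a common survival of 0.243.

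**Step 3: Boschloo at 0.20.** The cut-off on the Fisher p-value is 0.298. The maximum error is 0.173, at a common survival of 0.50. The next possible cut-off, 0.324, would give 0.209 and is not allowed.

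| Placebo survival | Power v 60%: Fisher | Power v 60%: Boschloo | Gain (points) | False positives if both arms have this survival: Fisher | Same: Boschloo |
|---|---|---|---|---|---|
| 10% | 96.1% | 98.0% | 1.9 | 5.4% | 15.4% |
| 20% | 82.7% | 90.3% | 7.6 | 10.7% | 16.6% |
| 30% | 62.2% | 75.4% | 13.2 | 10.6% | 15.9% |
| 40% | 40.1% | 55.1% | 15.0 | 9.6% | 16.8% |

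**Step 4: what changes.** Boschloo rejects wherever Fisher does and adds ten outcomes (duvelisib v placebo survivors): 2 v 0, 3 v 1, 6 v 3, 7 v 4, 8 v 5, 9 v 6, 10 v 7, 11 v 8, 13 v 11 and 14 v 12. For 8/14 v 5/14, the Fisher tail is Σ C(14,k)·C(14,13−k) for k = 8 to 13, divided by C(28,13): 8,414,784 / 37,442,160 = 0.225. The Boschloo p-value is 0.172.

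**Step 5: unequal splits.** Assume one unstratified list in 1:1 blocks of 10, with the third block stopped after 8. The arms can then be 14/14, 15/13 or 13/15. At 15/13 and 13/15, Fisher has maximum error 0.110 and power 84.0% or 83.7% (20% v 60%) and 41.5% (40% v 60%). Boschloo has maximum error 0.193 and power 91.0% or 91.7%, and 55.9%.

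**Step 6: two-sided Fisher, 14 v 14.** At 0.20, power is 69.3% and 26.2%. At 0.05 it is 44.3% and 9.0%.

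**The case against.** The strongest reply is that nothing is broken. The 0.20 in 12.1 is a ceiling that the sponsor need not use up; Fisher respects it and gives the stated power. The study is a hypothesis-generating pilot sized largely on feasibility, 12.1 calls for confirmatory studies whatever the result, and no decision is tied to p < 0.20. The power gain is also bought with error: at 10% common survival, false positives nearly triple for 1.9 points of power. All of this is right, and it is why the point is an option and not a fault. It does not remove the gain, because the plan does test, does state power, and set the ceiling itself.

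Three smaller objections also stand:

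- Some added outcomes look thin. At 13 duvelisib and 15 placebo patients, twelve outcomes are added, including 10/13 v 9/15 and 13/13 v 13/15.
- If Fisher is kept as a sensitivity result, its p-value will exceed 0.20 in every added outcome (0.210 to 0.298 at 14 v 14), so the two tests will disagree exactly where the gain arises.
- 12.1 says less than 0.20, not 0.20. If a lower level was meant, the figures for Boschloo at 0.20 do not apply, and the comparison must be redone at that level.

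On the drafting point, 12.1 directly precedes 12.2 and states a one-sided level for this endpoint, so the two-sided readings require departing from it. The gap is real but small.

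**Conclusion.** The concern holds as a low-cost improvement. Fisher's test at one-sided 0.20 is valid and meets 12.1. Boschloo's test at the same level is at least as powerful everywhere and stays under the limit: the maximum error rises from 0.111 to 0.173 (0.193 at 15/13 or 13/15). The gain is about 8 to 15 points for control survival of 20-40%, and only 1.9 points at 10%. Whether it is worth the extra false positives is for the sponsor to judge.

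The missing side and level in 12.2 are a drafting gap. Its worst plausible consequence is a two-sided test at 0.05, with power of 44.3% against a stated figure above 80%.

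These conclusions assume that 0.20 is the intended level, that arm sizes are 14/14 or within one of it, and that survival on duvelisib is 60% in the power figures.

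**What to change.** In 12.2:

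1. State that the primary test is one-sided, in favour of duvelisib, at 0.20, and make 12.1 give the same exact level.
2. Consider naming Boschloo's exact test, with the one-sided Fisher p-value as its ordering statistic, as the primary test. If adopted, restate power in 12.1 as about 90% (20% v 60%) and about 55% (40% v 60%), with maximum error about 0.17 (0.19 at 15/13 or 13/15).
3. Report Fisher's p-value as a sensitivity result, and say beforehand that the two may fall on opposite sides of 0.20 and that Boschloo governs.

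If the sponsor keeps Fisher, item 1 alone closes the drafting gap.

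**Cost.** The change is to wording in two sections, with no extra patients or visits; the test is in standard software. It is still a protocol modification, and Section 13 allows 4 weeks to forward it to secondary sites, 4 for local submission and 2 to return the approval documents, against a projected 3 months of enrolment. Section 11 has the study team preparing monitoring reports that include efficacy measures, so the choice must be fixed before anyone involved in it sees outcomes by arm. The statistical price is the higher false-positive rate, still below 0.20.
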